## **7. STUDY PROCEDURES**

### **7.1 Informed Consent**

All subjects must take part in the informed consent process. Adequate time must be allowed for the subject to ask questions and make a voluntary decision. No protocol-specific procedures, including screening procedures are to be performed until the subject has signed and dated an IRB-approved ICF. Subjects may withdraw consent at any time. Participation in the study may be terminated at any time without the subject's consent as determined by the Investigator.

### **7.2 Demographics and Medical History**

Demographics (age, gender, race and ethnicity) and medical history will be obtained from the subject and recorded on the source document and electronic case report form (eCRF). Medical history will capture the subject's current medical history (current disease processes), past medical status (past disease processes), history of surgery, concomitant treatments, and relevant clinical response to past disease specific treatments including duration and dosing of such treatments.

### **7.3 Physical Examination**

A complete physical examination will include measurements of weight (in kg) and height (in cm; height to be measured only at screening visit) and a review of the following body systems:

- General appearance
- Head, eyes, ears, nose, and throat
- Neck
- Respiratory
- Cardiovascular
- Abdomen
- Neurologic
- Extremities
- Dermatologic
- Lymphatic

Any abnormal and clinically significant findings from the physical examination must be recorded in the appropriate eCRF. Findings at screening and Day 0 (pre-dose) will be recorded as medical history.

### **7.4 Vital Sign Measurements**

Vital sign assessments will include measurements of sitting blood pressure (mm Hg), heart rate (beats per minute), respiration rate (breaths per minute), pulse oximetry, and oral temperature (Celsius). Abnormal results are to be repeated after 5 minutes of rest. See [Table 6](#) for timing window allowances with respect to measurement collection.

Vital sign measurements will be collected after the subject has been sitting for 5 minutes. Subjects should be seated quietly for at least 5 minutes in a chair with their backs supported, their feet flat on the floor (legs uncrossed), and their arms bared on a hard surface, with the arm slightly abducted and bent, with palm up and the midpoint of upper arm at heart level. Correct cuff and bladder size should be utilized and the same cuff and arm should be used per subject throughout study.

Vital sign measurements are to be obtained immediately prior to the infusion; 15, 30, and 45 minutes after the start of the infusion; at completion of the infusion; 30 minutes, 1 hour, and 2 hours following completion of the infusion. Abnormalities in vital sign measurements will be graded in severity per the National Cancer Institute Common Terminology Criteria for Adverse Events (NCI CTCAE) scale Version 4.03.

**Table 6. Timing Windows for PK/PD Sampling, ECG, and Vital Sign Measurements**

Time Point	Tolerance Window	
	Cohort 1	Cohorts 2, 3, and 4 (Optional Cohort)
Pharmacokinetic Sampling		
0 hour	-240 minutes to 0 hour	-240 minutes to 0 hour
5 minutes post end-of-infusion	±5 minutes	±5 minutes
1 hour post end-of-infusion	N/A	±15 minutes
2 hours post end-of-infusion	±15 minutes	±15 minutes
4 and 6 hours post end-of-infusion	±15 minutes	N/A
24 hours (1 day) post end-of-infusion	±60 minutes	N/A
48 hours (2 days) post end-of-infusion	±120 minutes	N/A
Pharmacodynamic Sampling		
0 hour	-240 minutes to 0 hour	-240 minutes to 0 hour
24 hours (1 day) post end-of-infusion	±60 minutes	N/A
48 hours (2 days) post end-of-infusion	±120 minutes	N/A
ECG		
5 minutes post end-of-infusion	±10 minutes	±10 minutes
Vital Signsa		
0 hour	-240 minutes to 0 hour	-240 minutes to 0 hour
15, 30, and 45 minutes after start of infusion	±5 minutes	±5 minutes
1 hour after start of infusion	±10 minutes	±10 minutes
30 minutes, 1 and 2 hours post end-of-infusion	±10 minutes	±10 minutes

Abbreviations: ECG = electrocardiogram; N/A = not applicable; PD = pharmacodynamic; PK = pharmacokinetic.

a. Vital signs to include blood pressure, pulse rate, respiratory rate, oral temperature, and pulse oximetry.

## 7.5 Clinical Laboratory Measurements

Laboratory testing (hematology, urinalysis, serum chemistry, virology, serology, pregnancy tests, PD samples, PK samples, and ADA samples) will be performed using established methods by a central laboratory. Clinical safety laboratory panels are listed in Table 7. Blood and urine samples for hematology, serum chemistry, and urinalysis will be prepared using standard procedures. Results will be provided to the Investigator. Aliquots from the PK, biomarker and ADA samples may be retained as back-up for additional testing as necessary. Subjects will be in a seated or supine position during blood collection. Collection times for all safety, PD, and exploratory labs are outlined in Table 2, Table 3, and Table 4.

**Table 7. Clinical Safety Laboratory Panels**

Hematology	Serum Chemistry	Urinalysis	Virology

 
CBC with differential and blood smear
 
Erythrocyte sedimentation rate
 
	
 
Albumin
 
Alkaline phosphatase
 
ALT
 
AST
 
BUN
 
C-Reactive Protein
 
Calcium
 
Carbon dioxide
 
Chloride
 
Creatinine
 
Glucose
 
LDH
 
Phosphorus
 
Potassium
 
Sodium
 
Total and direct bilirubin
 
Total protein
 
Uric acid
 
	
 
Appearance
 
Color
 
pH
 
Specific gravity
 
Ketones
 
Protein
 
Glucose
 
Nitrite
 
Urobilinogen
 
Blood/hemoglobin
 
Leukocyte esterase
 
Bilirubin
 
Microscopic examination of sediment: only if the results of the urinalysis dipstick evaluation are positive for blood/hemoglobin
 
	
 
Hepatitis C
 
Hepatitis B
 
HIV
 
Tetanus
 
VZV
 

Abbreviations: ALT = alanine aminotransferase; AST = aspartate aminotransferase; BUN = blood urea nitrogen; CBC = complete blood count; HIV = human immunodeficiency virus; LDH = lactate dehydrogenase; VZV = Varicella-Zoster virus.

Abnormalities in clinical laboratory tests that are considered clinically significant are to be recorded on the AE eCRF page. Laboratory results will be graded using the NCI CTCAE, Version 4.03. If laboratory values constitute part of an event that meets criteria defining it as serious, the event (and associated laboratory values) must be reported as an SAE (see Section 10.2.3).

For Cohort 1, the total blood draw for each subject who completes the study at Day 112 will be approximately 420 mL. For Cohort 2 the total blood draw for each subject who completes the study at Day 112 will be approximately 380 mL. For Cohort 3 and Cohort 4 (Optional), the total

blood draw for each subject who completes the study at Day 175 will be 656 mL. Please refer to the Laboratory Manual for more information.

### **7.5.1 Pregnancy Testing**

Pregnancy testing will be performed for women of childbearing potential. Urine or serum test is acceptable; however, positive urine tests must be confirmed with serum testing.

### **7.5.2 Virology**

Testing for hepatitis C antibody, hepatitis B surface antigen, and HIV antibody will be performed at screening.

### **7.5.3 Serum Tetanus Antibody and Varicella-Zoster Virus Antibody Testing**

Samples for serum tetanus antibody and VZV antibody testing are to be collected at baseline (pre-dose, Day 0), during the follow-up period, and at the end-of-study visit. Any subject whose baseline value for tetanus or VZV was above the detectable level at baseline, and is not within 30% of the baseline value or is below the protective level by the end-of-study visit, will be referred to their primary care physician for further management.

### **7.5.4 Pharmacokinetics (PK) Sampling**

The following PK parameters will be studied in Cohort 1:  $t_{1/2}$ ,  $C_{max}$ ,  $T_{max}$ ,  $AUC_{0-24}$ , and  $AUC_{0-\infty}$ . For all successive cohorts, the PK parameters studied will be  $C_{max}$  and  $T_{max}$ .

Specific collection times are detailed in [Table 6](#). Detailed instructions for sample collection and preparation will be provided in a separate laboratory manual

### **7.5.5 Pharmacodynamic Sampling**

PD samples will be collected for analyses throughout the study. Measurements for albumin will be derived from the clinical safety laboratory results. Specific collection times are detailed in [Table 8](#). Samples for each type of PD will be collected according to the schedule shown in [Table 8](#).

**Table 8. Pharmacodynamic Assessments**

Parameter	Collection Time Points		
	Cohort 1	Cohort 2	Cohort 3

 
IgG
 
IgG subtypes (IgG1-4)
 
IgA
 
IgM
 
	Screening and Days 0, 1, 2, 5, 7, 12, 14, 19, 21, 28, 29, 30, 33, 42, 56, 84, and 112	Screening and Days 0, 7, 14, 21, 28, 35, 42, 56, 84, and 112	Screening and Days 0, 7, 14, 21, 28, 35, 42, 49, 56, 63, 70, 77, 84, 91, 98, 105, 119, 147, and 175

 
Circulating immune complexes (CIC)
 
	Days 0, 5, 7, 12, 14, 19, 21, 28, 33, 42, 56, 84, and 112	Days 0, 7, 14, 21, 28, 35, 42, 56, 84, and 112	Days 0, 7, 14, 21, 28, 35, 42, 49, 56, 63, 70, 77, 84, 91, 98, 105, 119, 147, and 175

 
Albumin
 
	Screening and Days 0, 7, 14, 21, 28, 33, 42, 56, 84, and 112	Screening and Days 0, 7, 14, 21, 28, 35, 42, 56, 84, and 112	Screening and Days 0, 7, 14, 21, 28, 35, 42, 49, 56, 63, 70, 77, 84, 91, 98, 105, 119, 147, and 175

 
Anti-Dsg (1 and 3) antibody titers
 
	Screening and Days 0, 7, 14, 33, 56, 84, and 112	Screening and Days 0, 7, 14, 21, 28, 35, 42, 56, 84, and 112	Screening and Days 0, 7, 14, 21, 28, 35, 42, 49, 56, 63, 70, 77, 84, 91, 98, 105, 119, 147, and 175

 
C3 and AECA levels by indirect immunofluorescence
 
	Days 0, 14, 33, 56, 84, and 112	Days 0, 35, and 56	Days 0, 98, and 119

 
Exploratory biomarkers (RNAseq, urine IgG)
 
	Days 0, 14, 33, 56, 84, and 112	Days 0, 35, and 56	Days 0, 98, and 119

 
Immunophenotyping by flow cytometry for measurement of T cells, monocytes, NK cells, and B cells
 
	Days 0, 28, and 56	Days 0, 35, and 56	Days 0, 98, and 119

 
Exploratory biomarker (FCGR2A SNP, via buccal swab)
 
	Day 0	Day 0	Day 0

 
Exploratory pemphigus immune response biomarkers
 
	Days 0, 5, 7, 12, 14, 19, 21, 28, 33, 42, 56, 84, and 112	Days 0, 7, 14, 21, 28, 35, 42, 56, 84, and 112	Days 0, 7, 14, 21, 28, 35, 42, 49, 56, 63, 70, 77, 84, 91, 98, 105, 119, 147, and 175

See [Table 6](#) for timing window allowances with respect to measurement collection. More information, including detailed instructions for sample collection (including collection tubes) and preparation will be provided in a separate laboratory manual.

### 7.5.6 Immunogenicity Testing

SYNT001 is being developed for the acute and chronic therapy of autoimmune disorders. Although SYNT001 is a humanized IgG4 mAb, exposure to SYNT001 in clinical trials could result in the development of ADAs, with potential consequences ranging from neutralization with possible lessening of drug efficacy to safety consequences such as allergic reactions. Testing will first detect binding ADAs. Then, for all confirmed positive samples, an ADA titer will be determined and there will be testing for neutralizing effects.

More information, including detailed instructions for sample collection and preparation will be provided in a separate laboratory manual.

## 7.6 12-Lead Electrocardiogram (ECG)

On dose administration days, digital 12-lead ECG measurements will be obtained at 5 minutes after the completion of the infusion. All ECGs are to be performed with the subject in a supine position having rested in this position for at least 5 minutes before each reading. ECGs are to be performed in triplicate, each at an interval of 1 to 2 minutes apart. See [Table 6](#) for timing window allowances with respect to performing ECG.

The following ECG parameters will be collected: PR interval, RR interval, QRS interval, and QT interval. The ECG findings will be evaluated by a qualified physician for the presence of abnormalities (qualitative assessment). The physician will assess each ECG as normal, abnormal/not clinically significant, or abnormal/clinically significant.

Normal corrected QT interval using Fridericia's formula (QTcF) is  $\leq 450$  msec.

Abnormalities in the ECG that appear following therapy or that result in clinical signs and symptoms are considered clinically significant for the purposes of this study and will be recorded on the AE eCRF.

## 7.7 Pemphigus Disease Area Index (PDAI)

Pemphigus severity and disease activity will be measured using the PDAI in regions where a validated questionnaire is available. A PDAI total activity score will be determined at screening. To be eligible for study participation, the patient's grade by disease severity must be  $>4$ . Assuming subject eligibility, the PDAI will be administered during Treatment Period and Follow-up Period. Disease severity categories by PDAI are mild (0 to 8), moderate (9 to 24), and severe ( $\geq 25$ ) ([Shimizu et al., 2014](#)). The Investigator will determine a PDAI score as follows: 0 to 250 points for disease activity ( $\leq 120$  for skin,  $\leq 10$  for scalp, and  $\leq 120$  for mucosa), and 0 to 13 points for damage ( $\leq 12$  for skin and  $\leq 1$  for scalp) ([Rosenbach et al., 2009](#)). See [Appendix 2](#).

## 7.8 Study Drug Administration

SYNT001 will be given as a 250-mL IV infusion over 1 hour  $\pm$  15 minutes using a 0.2-micron, inline filter.

## 7.9 Photographs

Photographs will be taken of active lesions and follow-up photographs will be taken of the same areas at timepoints indicated in [Table 2](#), [Table 3](#), and [Table 4](#). Subjects who begin a steroid taper will have additional photographs taken at the clinic visit during which the decision to begin the taper is made. A separate manual describing the procedures for taking photographs will be provided.

## 7.10 Health-Related Quality of Life Assessments

For Cohorts 2, 3 and 4 (optional cohort), health-related quality of life will be assessed using ABQoL and Skindex-29 in regions where a validated questionnaire is available. The ABQoL questionnaire was developed in Australia as a patient-based measure to quantify disease burden, monitor disease activity and evaluate response to therapeutic intervention in patients with autoimmune bullous disease (Sebaratnam et al., 2013; Sebaratnam et al., 2015) (Appendix 3). Skindex-29 was developed to measure the effects of skin disease on patients' quality of life using a self-administered 30 question dermatology survey (Chren et al., 1996) (Appendix 4).

## 7.11 Adverse Event Assessments

Information regarding the occurrence of AEs will be collected from the time the subject signs the informed consent form and continuing through the last study visit. Findings at screening and Day 0 (pre-dose) will be recorded as medical history. Any known untoward event that occurs beyond the AE reporting period that the Investigator assesses as related to study drug also should be reported as an AE. Clinical AEs will be graded using the NCI CTCAE, Version 4.03 (Appendix 1).

**Note:** AEs resulting in a subject's permanent discontinuation from the study, regardless of seriousness or relationship to study drug, MUST be promptly reported to the Sponsor. Additionally, subjects must be followed until return to normal and/or resolution of the AE.

See Section 10 for more information.

## 7.12 Prior and Concomitant Medications

All treatments a subject receives within 14 days prior to enrollment through the end of the study will be documented on the source document and eCRF. A history of treatments taken for the primary disease, even if not taken within the 14 days prior to enrollment, will be collected.

### Permitted Medications

Concomitant medication and treatment for co-existing conditions, including those for pemphigus, are permitted if not listed as prohibited.

1. Topical antibiotics to treat active infections that occur during the study.
2. Topical or systemic treatments for oral candidiasis.
3. Topical lidocaine for transient pain relief as needed.
4. Concomitant treatment that is medically indicated for any AEs the subject experiences during the study.
5. Medication for potential infusion reactions: The Investigator may recommend prophylactic use of acetaminophen, IV hydration, diphenhydramine, histamine2 (H2) blockers (eg, ranitidine, famotidine), etc to manage potential infusion reactions.
6. Low-strength corticosteroids (eg, hydrocortisone ≤1%) applied to a single lesion contributing <10% of the PDAI total activity score.
7. Topical tacrolimus, sirolimus or pimecrolimus applied to a single lesion contributing <10% of the PDAI total activity score.

8. Dexamethasone elixir solution for oral lesions if dose remains stable throughout trial participation (swish and spit only).
9. Stable regimen of the following systemic immunosuppressants: azathioprine, mycophenolate mofetil, methotrexate, dapsone, cyclosporine, tacrolimus, sirolimus, or low dose oral cyclophosphamide ( $\leq 100$  mg/day).

One month after the final dose of SYNT001, corticosteroids may be tapered at the Investigator's discretion.

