## 1. SYNOPSIS

Study title	A Phase 1b/2, Multicenter, Open-Label, Safety, and Dose-Finding Study of SYNT001 in Subjects with Pemphigus (Vulgaris or Foliaceus)
Sponsor	Syntimmune, Inc.
Protocol number	SYNT001-103
Clinical phase	Phase 1b/2
Number of study centers	Approximately 10 global study sites
Study rationale	
Pemphigus is a potentially life-threatening group of rare blistering autoimmune diseases that affect the skin and mucous membranes. The exact cause is unknown, though autoantibodies are thought to play an important pathogenic role in the mucosal and cutaneous manifestations in patients with pemphigus.
 
The prognosis of pemphigus has markedly improved over the last decades with steroid therapy. Nevertheless, mortality remains an issue (1.6% to 12% of cases) (Hsu et al., 2016; Kasperkiewicz et al., 2017; Langan et al., 2008). In these cases, death typically occurs as a consequence of treatment-related systemic infections and in a smaller proportion, as a consequence of superinfected lesions. While steroids have greatly improved patient outcomes, they are associated with serious and long-lasting side effects; therefore, their use should be limited as much as possible. Although other currently available treatments for certain autoimmune disorders, including immunosuppressants, intravenous immunoglobulin (IVIG), plasmapheresis, and anti-CD20 monoclonal antibodies (mAbs), such as rituximab, can be effective, they can be associated with significant adverse effects and delayed or non-durable responses.
 
SYNT001 targets key mechanisms contributing to pathology in a variety of immunoglobulin G (IgG)-mediated autoimmune disorders. When administered to healthy subjects, SYNT001 has been shown to significantly decrease total IgG, as well as immune complexes with which IgG is associated. Based on these results, it is predicted that SYNT001 will also reduce the levels of pathogenic autoantibodies. This could lead to a decrease in the mucosal and cutaneous manifestations in patients with pemphigus. Moreover, the ability of SYNT001 to reduce circulating immune complexes (CICs) and the associated innate and adaptive immune responses may allow for sustained disease modification. Thus, this study is being conducted to evaluate the safety and immunogenicity and determine a minimally effective dose (MED) of intravenous (IV) SYNT001 in pemphigus patients.

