	
The treatment period includes the Baseline (Day 0) Dosing Visit day, and Major and Minor Dosing Visit days. Refer to Table 2, Table 3, Table 4, and Section 7.
 
Baseline (Day 0) Visit Day
 
In addition to the safety and tolerability assessments described above, the subject will be administered the study drug and the following procedures will be conducted: pregnancy test (if applicable), PDAI, PK, PD, and immunogenicity sample collection, photography of lesions, and serum tetanus and varicella zoster virus (VZV) antibody tests. An optional skin biopsy may be collected. HR-QoL is assessed in all cohorts except Cohort 1. A complete list of assessments is provided in Table 2, Table 3, Table 4, and Section 7.
 
Major Dosing Visit Days
 
In addition to the safety and tolerability assessments described above, the subject will be administered the study drug, and the following procedures will be conducted: PDAI, PD, and immunogenicity sample collection. A complete list of assessments is provided in Table 2, Table 3, Table 4, and Section 7.
 
Minor Dosing Visit Days
 
In addition to the safety and tolerability assessments described above, the subject will be administered the study drug, and the following procedures will be conducted: PDAI and PD sample collection. A complete list of assessments is provided in Table 2, Table 3, Table 4, and Section 7.
 
Follow-up Period/End of Study (84 days)
 
The follow-up period includes the Major and Minor Follow-up Visit days. Subjects are encouraged to participate in all visits up to and including Day 112 (Cohorts 1 and 2) or Day 175 (Cohort 3) to ensure study completion. Refer to Table 2, Table 3, Table 4, and Section 7.
 
Major Follow-up Visit Days
 
In addition to the safety and tolerability assessments described above, the following procedures will be conducted: PDAI, PD sample collection, photography of lesions and HR-QoL assessments. A complete list of assessments is provided in Table 2, Table 3, Table 4, and Section 7.
 
Minor Follow-up Visit Days
 
In addition to the safety and tolerability assessments described above, the following procedures will be conducted: PDAI and PD sample collection. A complete list of assessments is provided in Table 2, Table 3, Table 4, and Section 7.
 
Dosing for any individual subject will be discontinued (ie, further treatment with the study drug will not be given) if the subject experiences any study drug-related SAE or any study drug-related non-serious adverse event that, in the judgement of the Investigator (following consultation with the Medical Monitor, if desired) suggests that it could be unsafe to administer further study drug to that subject. Additionally, a subject will be discontinued from further treatment with study drug at the discretion of the Investigator, with consultation with the Medical Monitor if desired, if they require a significant increase in anti-pemphigus medications for the management of pemphigus.

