Permitted and prohibited concomitant treatments	
All treatments a subject receives within 14 days prior to enrollment through the end of the study will be documented.
 
Permitted Medications
 
Concomitant medication and treatment for co-existing conditions, including those for pemphigus, are permitted if not listed as prohibited.
 
 
1. Topical antibiotics to treat active infections that occur during the study.
 
2. Topical or systemic treatments for oral candidiasis.
 
3. Topical lidocaine for transient pain relief as needed.
 
4. Concomitant treatment that is medically indicated for any AEs the subject experiences during the study.
 
5. Medication for potential infusion reactions: The Investigator may recommend prophylactic use of acetaminophen, IV hydration, diphenhydramine, histamine2 (H2) blockers (eg, ranitidine, famotidine), etc to manage potential infusion reactions.
 
6. Low-strength corticosteroids (eg, hydrocortisone ≤1%) applied to a single lesion contributing <10% of the PDAI total activity score.
 
7. Topical tacrolimus, sirolimus or pimecrolimus applied to a single lesion contributing <10% of the PDAI total activity score.
 
8. Dexamethasone elixir solution for oral lesions if dose remains stable throughout trial participation (swish and spit only).
 
9. Stable regimen of the following systemic immunosuppressants: azathioprine, mycophenolate mofetil, methotrexate, dapsone, cyclosporine, tacrolimus, sirolimus, or low dose oral cyclophosphamide (≤100 mg/day).
 
 
One month after the final dose of SYNT001, corticosteroids may be tapered at the Investigator's discretion. Prohibited Medications
 
Use of the following medications will not be permitted during the study unless specified above as permitted:
 
 
1. Rituximab or other anti-CD20 antibody
 
2. Monoclonal antibodies other than study drug
 
3. Any topical or systemic immunosuppressive drugs apart from those that are listed as permitted.
 
4. IV corticosteroids prior to infusion (except in subjects who received corticosteroids for treatment of a prior infusion reaction to SYNT001)
 
5. Any dietary herbal supplements
 
6. Any investigational drug or device
 
7. Vaccinations within 2 weeks of screening through 28 days following final dose of study drug
 
																										

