### 6.3 Exclusion Criteria

A subject who meets any of the following criteria is ineligible for the study:

1. Subject unable or unwilling to comply with the protocol.
2. Active non-hematologic malignancy or history of non-hematologic malignancy in the 3 years prior to screening (exclusive of non-melanoma skin cancer and cervical cancer in situ).
3. Positive for human immunodeficiency virus (HIV) or hepatitis C antibody.
4. Positive for hepatitis B surface antigen.
5. Active infection or history of recurrent infections.
6. IVIG treatment within 30 days of screening.
7. Received any cytotoxic (other than azathioprine) or any non-anti-CD20 mAb therapy in the 3 months prior to screening.
8. Any exposure to an investigational drug or device within the 30 days prior to screening.
9. Plasmapheresis or immunoadsorption within 30 days of screening.
10. Cellular therapy, including chimeric antigen receptor and T-cell (CAR-T), at any time prior to screening.
11. Use of any systemic or topical immunosuppressive drugs within 3 months of screening not including dose allowed by the inclusion criteria.
12. Serum total IgG  $< 600$  mg/dL.

13. Subject has any current medical condition that, in the opinion of the Investigator, may compromise their safety or compliance, preclude successful conduct of the study, or interfere with interpretation of the results (eg, a significant pre-existing illness or other major comorbidity that the Investigator considers may confound the interpretation of the study results).
14. Any vaccination within 2 weeks of screening.

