### **Prohibited Medications**

Use of the following medications will not be permitted during the study unless specified above as permitted:

1. Rituximab or other anti-CD20 antibody
2. Monoclonal antibodies other than study drug
3. Any topical or systemic immunosuppressive drugs apart from those that are listed as permitted.
4. IV corticosteroids prior to infusion (except in subjects who received corticosteroids for treatment of a prior infusion reaction to SYNT001)
5. Any dietary herbal supplements
6. Any investigational drug or device
7. Vaccinations within 2 weeks of screening through 28 days following final dose of study drug

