## 9. STUDY RULES

### 9.1 Subject Withdrawal

Every reasonable effort will be made to keep the subject in the study; however, if a subject withdraws from the study, the Investigator should complete and report the reasons for withdrawal as thoroughly as possible. The reason(s) for termination must be clearly documented on the appropriate page of the eCRF.

If a subject discontinues from the study for any reason, every effort will be made to collect all clinical and laboratory data as scheduled for the Early Termination Visit (see [Section 8.4](#)). If the subject fails to return for these assessments for unknown reasons, every effort (eg, telephone, email, and letter) should be made to contact them.

The reason(s) for a subject's participation in the study may be prematurely discontinued will be documented and include:

1. The subject wishes to withdraw from the study.
2. Request by a regulatory agency (eg, Institutional Review Board).
3. The subject experiences a significant or intolerable AE.
4. The subject experiences a significant adverse change in vital signs, physical examination findings, or clinical laboratory parameter.
5. The subject has a need for a concomitant medication that is not permitted by the study protocol.
6. The subject experiences generalized impairment or mental incompetence that would result in the subject being unable to understand his or her participation in the study.
7. If, in the Investigator's medical judgment, further participation would be injurious to the health and well-being of the subject, or is not in the best interest of the subject.
8. Administrative reasons, such as subject non-compliance or a major protocol violation.
9. The subject requires a significant increase in dose(s) of anti-pemphigus medication(s) for the management of pemphigus (at the discretion of the Investigator with consultation with the Medical Monitor).

If at the discretion of the Investigator with consultation with the Medical Monitor, a subject requires a significant increase in dose(s) of anti-pemphigus medication(s) for the management of pemphigus, the subject will be encouraged to continue their study visits to allow collection of safety data.

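### Apheresis, and IVIG given for pemphigus, are allowed during the study by the default rule in Section 7.12, although both are washed out at entry and can alter the dose-selection measures

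*Protocol*

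**What the plan says.** Protocol Section 7.12, Permitted Medications, and the matching synopsis row state: "Concomitant medication and treatment for co-existing conditions, including those for pemphigus, are permitted if not listed as prohibited". The prohibited list opens with "Use of the following medications will not be permitted during the study unless specified above as permitted" and has seven items: anti-CD20 antibodies; other monoclonal antibodies; item 3, "Any topical or systemic immunosuppressive drugs apart from those that are listed as permitted"; IV corticosteroids before infusion; herbal supplements; investigational products; and vaccinations.

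Section 6.3 lists as exclusion 6 "IVIG treatment within 30 days of screening" and as exclusion 9 "Plasmapheresis or immunoadsorption within 30 days of screening".

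The nearest on-study control is a discretionary rule. In the synopsis (Study methodology), the investigator may stop study drug for subjects "if they require a significant increase in anti-pemphigus medications for the management of pemphigus". Section 9.1 item 9 gives a matching withdrawal reason: "The subject requires a significant increase in dose(s) of anti-pemphigus medication(s) for the management of pemphigus". Section 10.3.3 foresees IVIG for a bacterial infection while IgG is low. That use is not in question here.

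**The concern.** Most entry restrictions on treatment have an on-study counterpart. Exclusions 6 and 9 have none, so therapies judged important enough to wash out may be started from Day 0 onward.

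This matters because Section 3.4 bases dose selection on the total IgG nadir (a fall of 60% to 90%) and on a PDAI activity reduction of at least 50%. There is no control arm. The Dose Escalation Committee also uses total IgG when it recommends doses (Table 5 footnote). The protocol itself links apheresis to both measures. Section 2.2 relates its IgG target to remission under immunoadsorption in pemphigus vulgaris, and Section 10.3.3 cites IgG reductions of up to 95% with immunoadsorption. A nadir is a single lowest value, so one course of apheresis could set it. The resulting IgG fall, and any PDAI improvement, could then be credited to SYNT001.

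**Working it through.** The protocol gives no figure to reproduce. The check compares the texts and then works out the effect on the IgG band.

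**1. Entry restrictions against the on-study list**

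| Entry restriction | On-study prohibition |
|---|---|
| Anti-CD20 (6.2 item 4a) | item 1 |
| Other monoclonal antibodies (6.3 item 7) | item 2 |
| Immunosuppressive drugs (6.3 item 11) | item 3 |
| Investigational products (6.3 item 8) | item 6 |
| Vaccination (6.3 item 14) | item 7 |
| IVIG (6.3 item 6) | none |
| Plasmapheresis, immunoadsorption (6.3 item 9) | none |

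**2. Whether other text closes the gap**

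- *Prohibited item 3.* The study rationale names the available treatments as separate classes: "including immunosuppressants, intravenous immunoglobulin (IVIG), plasmapheresis, and anti-CD20 monoclonal antibodies (mAbs), such as rituximab, can be effective". On that usage IVIG is not an immunosuppressant, and apheresis is not a drug.
- *Significant-increase rule.* It is discretionary and speaks of medications, and in Section 9.1 of their doses. Starting IVIG can be read as such an increase. Starting a procedure does not clearly fit.
- *Section 9.1 item 5.* It applies to a medication the protocol does not permit. Under the default rule these treatments are permitted.
- *Permitted item 4.* It allows treatment medically indicated for any adverse event, and Section 10.2 counts the worsening of an existing condition as an adverse event. A pemphigus flare therefore opens a direct route. Because the prohibited list gives way to anything specified as permitted, adding names alone would not close it.

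**3. Effect on the IgG band**

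Let *d* be the drug-related fall and *x* the fraction of the remaining IgG removed by apheresis. Then

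total fall = 1 − (1 − *d*)(1 − *x*).

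The subject is in the band when 0.60 ≤ total ≤ 0.90, that is, for *x* from 1 − 0.40/(1 − *d*) to 1 − 0.10/(1 − *d*). A lower limit at or below zero means the subject is already in the band.

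| *d* | Source | Lower limit of *x* | Upper limit of *x* |
|---|---|---|---|
| 0.80 | 10.3.3, upper estimate, multiple doses | already in band | 1 − 0.10/0.20 = 0.50 |
| 0.70 | 10.3.3, as above | already in band | 1 − 0.10/0.30 = 0.667 |
| 0.60 | band edge | already in band | 1 − 0.10/0.40 = 0.75 |
| 0.55 | assumed | 1 − 0.40/0.45 = 0.111 | 1 − 0.10/0.45 = 0.778 |
| 0.50 | 2.2, single 30 mg/kg dose, healthy volunteers | 1 − 0.40/0.50 = 0.20 | 1 − 0.10/0.50 = 0.80 |
| 0.40 | assumed | 1 − 0.40/0.60 = 0.333 | 1 − 0.10/0.60 = 0.833 |

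At or above a 60% drug-related fall, apheresis either leaves band status unchanged or pushes the total above 90%. Below 60%, a wide range of removal brings the subject into the band.

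**The case against.** The sponsor has a fair reply on several points.

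- *Stable background therapy is plainly intended.* Systemic immunosuppressants must stay on a stable regimen, and escalation can end study drug. A reader might infer that nothing in the protocol restrains these therapies. For IVIG that goes too far. For apheresis the reply is weaker, because the rule is worded around medication.
- *Any session would be recorded.* Section 7.12 requires all treatments to be documented, and the Dose Escalation Committee may look at all available data. How later values are analysed can be left to the SAP. This stands, but documentation prevents nothing, and neither it nor the SAP can recover an IgG or PDAI value under the drug alone.
- *The trial gives 5 or 14 weekly doses (up to 14 in optional Cohort 4).* A reader might infer that apheresis would routinely turn non-responders into IgG successes. The documents do not support that. The 50% figure is a single-dose average in healthy volunteers, and at the 70% to 80% upper estimate the subject is already in the band. Section 11.4.3.2 also plans descriptive summaries, not a count of subjects in the band; the response proportion in Section 3.1 concerns PDAI.
- *IVIG adds IgG.* A reader might infer that IVIG too would exaggerate the IgG fall. It works the other way on IgG. It could still affect PDAI, but the documents give no size.

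A reader might also infer that prohibited item 3 bars the systemic corticosteroids admitted by inclusion criterion 4c. That does not hold: item 4's narrower ban on IV corticosteroids would then be redundant, and both the taper sentence in Section 7.12 and the corticosteroid-use endpoint presuppose continued use.

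**Conclusion.** The concern holds as a narrow but real gap in a stated rule. Followed literally, Section 7.12 allows plasmapheresis and immunoadsorption on study, and allows IVIG for pemphigus unless the discretionary rule is invoked. It should be fixed, mainly for apheresis.

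The size is conditional. If the drug-related IgG fall reaches 70% or 80%, apheresis changes band status only by removing more than 67% or 50% of the remainder, and then by pushing the subject above 90%. If the fall is below 60%, apheresis can create apparent success on IgG. These results assume that apheresis removes a fixed fraction of the IgG left at the nadir, with no rebound. For scale on PDAI, one subject is 1/4 = 25 percentage points of the response proportion in a cohort of 4, or 1/8 = 12.5 points if it is expanded to 8.

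The documents do not say how often such rescue would occur. They support no claim that dose selection will be biased by a given amount, and no effect size for PDAI or IVIG.

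**What to change.** - In Section 7.12 and the synopsis, head the list *Prohibited medications and treatments* and add plasmapheresis, immunoadsorption and IVIG, except IVIG for infection with low IgG under Section 10.3.3. Apply this from screening through the end-of-study visit: Day 112 for Cohorts 1 and 2, Day 175 for Cohort 3, and the corresponding visit for optional Cohort 4.
- State that permitted item 4 does not override this when the adverse event is worsening pemphigus.
- In Section 9.1 item 5, add *or treatment* after *medication*, and say there that a subject who needs such rescue may receive it but stops study drug and continues visits for safety.

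The handling of IgG and PDAI values after rescue can stay with the SAP.

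The cost is a few lines in three places, through a protocol amendment with IRB approval (Section 12.4). The downside is fewer evaluable IgG and PDAI values from rescued subjects. Care is not withheld, since rescue remains available once study drug is stopped.
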